2.3. Study Plan

Study Visits

The study consists of a screening period of up to 30 days (Screening Period), followed by a 7 to 10 day pre-randomization period (Pre-Randomization Period), a 16-week randomized, double-blind, placebo-controlled treatment period (Treatment Period 1), a 36-week, double-blind, placebo-controlled treatment period (Treatment Period 2) in which non-NSAID standard-of-care pain medications can also be used in the event of inadequate pain relief for OA pain, a 24-week follow-up period, and an end of study phone contact at 52 weeks following the last dose of study drug to determine whether a joint replacement (JR) has been conducted or is scheduled (or the patient is on a waiting list).

A subset of patients will also be participating in a 16-week efficacy sub-study to characterize the efficacy of fasinumab. Efficacy assessments will be performed during treatment period 1, which will be followed by the 36-week treatment period 2, and a 24-week follow-up period. See [Figure 1](#) for the Study Flow Diagram.

Figure 1: Study Flow Diagram

The Schedule of Events table is presented in [Appendix 11.1](#).

3. ANALYSIS POPULATIONS

In accordance with guidance from the International Council for Harmonisation of Technical Requirements for Registration of Pharmaceuticals for Human Use (ICH) guideline ICH E9 Statistical Principles for Clinical Trials (1998), the following populations will be used for all statistical analyses:

3.1. Full Analysis Set (FAS)

Efficacy sub-study

The full analysis set for the efficacy sub-study (FAS-substudy) includes all randomized patients in the efficacy sub-study. Efficacy analyses are based on the treatment allocated (as randomized).

LTS study

The full analysis set for the LTS study (FAS-LTS) includes all randomized patients in the overall study (randomized within either the efficacy sub-study or the main study). This analysis set will be used to summarize baseline characteristics and patient disposition; it is based on the treatment allocated (as randomized).

3.2. The Safety Analysis Set (SAF)

Efficacy sub-study

The safety analysis set for the efficacy sub-study (SAF-substudy) includes all randomized patients in the efficacy sub-study who received any study drug during the efficacy sub-study; it is based on the treatment received (as treated). Patients who receive at least one dose of fasinumab will be classified to the respective active treatment arm for the purpose of the analysis. Treatment compliance/administration and all clinical safety variables will be analyzed using the SAF-sub-study for the efficacy sub-study.

LTS study

The safety analysis set for the LTS study (SAF-LTS) includes all randomized patients in the overall study (randomized within either the efficacy sub-study or the main study) who received any study drug during the LTS study; it is based on the treatment-as-received (as treated). Patients who receive at least one dose of active fasinumab will be classified to the respective active treatment arm for the purpose of the analysis. Treatment compliance/administration and all clinical safety variables will be analyzed using the SAF for the entire study.

3.3. Per Protocol Set

Efficacy sub-study

PPS will include all FAS-sub-study patients who do not have major protocol deviations through week 16. The PPS will be used to perform sensitivity analyses for the primary and key secondary endpoints. Patients with the following major protocol deviations will be excluded from the PPS:

- Intolerance or Inadequate pain relief with analgesics assessment was not performed
- Analgesic medications administered during the week 16 treatment period prohibited by protocol
- Confirmed treatment unblinding that occurred in error.
- Study drug administered without a randomization record per IVR.
- Randomization without documented study eligibility

3.4. The Pharmacokinetic Analysis Set

The PK analysis set includes all treated patients who received any study drug and who had at least 1 non-missing drug concentration following the first dose of study drug.

3.5. The Anti-drug antibody Analysis Set

The ADA analysis set includes all treated patients who received any treatment and who had at least 1 non-missing post-dose ADA result.

4. ANALYSIS VARIABLES

4.1. Demographic and Baseline Characteristics

Baseline characteristics will include standard demography (e.g., age, sex, race, ethnicity, weight, height, etc.), disease characteristics including index joint, Kellgren-Lawrence score, WOMAC pain subscale score at screening, medical history, and medication history for each patient.

The following demographic and baseline characteristic variables will be summarized by treatment group:

- Age at screening (years)
- Age category (<65, >=65 years)
- Sex (Male, Female)
- Race (American Indian/Alaskan Native, Asian, Black/African American, Native Hawaiian/Other Pacific Islander, White, and Other)
- Ethnicity (Hispanic or Latino, Not Hispanic or Latino, Not Reported)
- Baseline Weight(kg)
- Baseline Height(cm)
- Baseline Body mass index (BMI) calculated from weight and height
- Index Joint (Knee or Hip)
- K-L score for the Index Joint
- WOMAC pain score of the index joint at screening
- Duration of OA at baseline
- History of analgesic intolerance and inadequate pain relief

Additional baseline characteristics will be summarized if needed.

4.2. Medical History

Medical history will be coded to a Preferred Term (PT) and associated primary System Organ Class (SOC) according to the latest available version of Medical Dictionary for Regulatory Activities (MedDRA®).

4.3. Prior/Concomitant Medications and Procedures, Prohibited Medication

Medications/Procedures will be recorded from the day of informed consent until the End of Follow-up Clinic Visit. Medications will be coded to the Anatomical Therapeutic Chemical (ATC) level 2 (therapeutic main group) and ATC level 4 (chemical/therapeutic subgroup), according to the latest available version of WHO Drug Dictionary (WHODD). Patients will be counted once in all ATC categories linked to the medication.

Medication/Procedure Classifications

Prior medications/procedures are defined as medications/procedures starting prior to the first dose of study drug.

Concomitant medications/procedures are defined as medications/procedures starting prior to or during each respective on-treatment period (as defined in Section 5.8) and ending during or after the respective on-treatment period.

Post treatment medications/procedures are medications/procedures starting after the on-treatment period (as defined in Section 5.8).

Prohibited Medication

Patients were required to discontinue all non-study pain medication (oral or topical; except up to 150 mg/day of aspirin/5-ASA, which is permitted for cardiac prophylaxis, per local guidelines) and opioid analgesic medications, starting at the pre-randomization phone call/visit.

Analgesic medications (including tramadol) were prohibited through week 16. Patients were directed not to take concomitant medications that contain NSAIDs (oral or topical, except up to 150 mg/day of aspirin/5-ASA, which is permitted for cardiac prophylaxis) during treatment period 1. Patients could have taken non-NSAID standard-of-care therapy in addition to study drug, in the event of inadequate pain relief for OA pain, starting after the week 16 visit. Though use of oral NSAIDs should generally be avoided, a limited use is allowed after week 16 for non-OA related pain or fever after week 16. A list of medications containing NSAIDs will be provided in the study reference manual. The dose of oral NSAIDs may be increased and topical NSAIDs may be used during the follow-up period, but no earlier than 16 weeks after the last dose of study drug.

Other excluded drugs during treatment period 1 are:

- Medical marijuana
- Hyaluronic Acid Intra-articular Injections
- Cyclobenzaprine, carisoprodol, orphenadrine, tizanidine

For efficacy sub-study only during treatment period 1:

- Glucosamine sulfate
- Chondroitin sulfate

Other excluded drugs during both treatment periods 1 and 2 are:

- Any other investigational agent
- Corticosteroids (topical and inhaled formulations are permitted)
- Cyclosporine
- Azathioprine
- Tumor necrosis factor antagonists
- IL-1 inhibitors, including diacerein
- IL-6 or IL-6 receptor antagonists
- Abatacept

4.4. Efficacy Variables for the Efficacy sub-study

4.4.1. Primary Efficacy Variable(s)

The co-primary efficacy endpoints assessed for the efficacy sub-study only are:

- Change from baseline to week 16 in the WOMAC pain subscale score
- Change from baseline to week 16 in the WOMAC physical function subscale score

4.4.2. Key Secondary Efficacy Variable(s)

The key secondary efficacy endpoints assessed for the efficacy sub-study only are:

- Change from baseline to week 16 in the Patient Global Assessment for OA score
- Percentage of patients who had a response at week 16, with response defined as an improvement by $\geq 30\%$ in WOMAC pain subscale score

4.4.3. Additional Secondary Efficacy Variable(s)

The additional secondary efficacy endpoints to be assessed in the efficacy sub-study only are:

- Change from baseline to week 16 in the average weekly walking index joint pain using the NRS pain scale

4.5. Safety Variables

Patient safety will be assessed through the collection of reported adverse events (AEs), clinical laboratory data, vital signs, ECG, Survey of Autonomic Symptoms Questionnaire, neurological exams and physical exams. Unless otherwise noted, the baseline value is defined as the last available value before the first dose of study drug.

Adverse events (AE) and Serious Adverse Events (SAE) will be collected from the time of informed consent signature and then at each visit until the End of Follow-up Clinic Visit. All AEs are to be coded to a “Preferred Term (PT)” and associated primary “System Organ Class SOC” according to the MedDRA[®] (the latest current available version).

An Adverse Event is any untoward medical occurrence in a patient or clinical investigation patient administered a pharmaceutical product and which does not necessarily have to have a causal relationship with this treatment.

A Serious Adverse Event is an adverse event (AE) that is classified as serious according to the criteria specified in the protocol.

Laboratory results, vital signs, or ECG abnormalities are to be recorded as AEs if they are medically relevant: symptomatic, requiring corrective therapy, leading to treatment discontinuation and/or fulfilling a seriousness criterion.

4.5.1. Primary Safety Variables

The primary safety endpoint in the study is safety monitoring including AE incidence, SAE, incidence, AESI incidence, changes in safety lab analyses, and incidence of anti-fasimumab antibody formation from baseline to week 52 (treatment period 1 and 2) and to week 72 (end of follow-up period).

More specifically, this includes:

- Incidence of adjudicated arthropathy events
- Incidence of destructive arthropathy events
- Incidence of JR (All JRs and AESI JRs) events – including endpoint for all JRs by the telephone survey approximately 52 weeks after the last dose of study drug
- Incidence of peripheral neurosensory AESI events

- Incidence of sympathetic nervous system dysfunction AESI events
- AE incidence, SAE incidence, changes from baseline in safety laboratory analyses, and incidence of anti-fasimumab antibody formation
- Change from baseline in minimum joint space width of the index joint (knee, hip)
- Incidence of confirmed orthostatic hypotension from baseline

The raw incidence rate is defined as the number of events divided by the duration of the observation period and presented as number of events per 100 patient-years.

4.5.2. Exploratory Safety Variables

Exploratory safety endpoints include:

- The proportion of patients taking rescue medication, number of days on rescue medication, and weekly average usage of rescue medication from baseline to week 16 and from baseline to week 52
- The percent of patients using standard-of-care analgesic medication from week 16 to week 52
- Time to joint replacement (JR) decision
- Survey of Autonomic Symptom scores from baseline to week 52 and from baseline to week 72
- Time to AA, time to DA

4.5.3. Adverse Events of Special Interest

An AESI (serious or non-serious) is one of scientific and medical concern specific to the sponsor's product or program, for which ongoing monitoring and rapid communication by the investigator to the sponsor can be appropriate.

AESI are selected using e-CRF specific tick box on the AE page.

Events considered to be AESIs for the study are:

- Adjudicated arthropathy (as confirmed by adjudication)
- Sympathetic nervous system dysfunction (as diagnosed after consultation with an appropriate specialist, such as a neurologist and/or cardiologist)
- Peripheral sensory AEs that require a neurology or other specialty consultation

- JR surgery (AESI defined in Protocol Section 7.6.1.4 as elective JR surgery not due to new or worsening disease)

4.5.4. Laboratory Safety Variables

The clinical laboratory tests include blood chemistry, hematology, urinalysis, urine chemistries, hs-CRP, and others. Samples for laboratory testing will be collected at the time points specified in the Schedule of Events ([Appendix 11.1](#)). Clinical laboratory values will be in standard international (SI) units, including associated normal ranges provided by the central laboratory, and grouped by function in summary tables. Clinical laboratory values in conventional (US) units will also be available in the database, with associated normal ranges.

Both actual test values and “change from baseline” values (defined as the post-baseline value minus the baseline value) will be used in central lab result summaries. Potentially clinically significant values (PCSV) ranges will be applied to central lab test values as applicable (see [Appendix 11.2](#) for PCSV definitions).

4.5.5. Biomarker variables

Biomarker analysis will be performed in a separate biomarker SAP.

4.5.6. Vital Signs

The following vital signs parameters will be collected at according to the Schedule of Events in [Appendix 11.1](#):

- Body temperature (°C)
- Sitting/supine/standing/orthostatic systolic and diastolic blood pressures (mmHg) and pulse (bpm)
- Respiratory rate (bpm)

Both actual values and “change from baseline” values (defined as the post-baseline value minus the baseline value) will be used in the result summaries. Potentially clinically significant values (PCSV) ranges will be applied to the vital sign parameter values as applicable (see [Appendix 11.2](#) for PCSV definitions).

4.5.7. Orthostatic Hypotension

A patient will be determined to have orthostatic hypotension if any of the following criteria are met:

- If the supine blood pressure is <160 mmHg systolic, a decrease in either the 1 or 3 minute standing systolic blood pressure of ≥ 20 mmHg or a decrease in the standing diastolic blood pressure of ≥ 10 mmHg from the supine systolic or diastolic blood pressure

OR

- If the supine blood pressure is ≥ 160 mmHg systolic, a decrease in either the 1 or 3-minute standing systolic blood pressure of ≥ 30 mmHg or a decrease in the standing diastolic blood pressure of ≥ 15 mmHg from the supine systolic or diastolic blood pressure

OR

- An increase in either the 1 or 3-minute standing heart rate of ≥ 30 bpm from the supine heart rate

OR

- The patient is unable to stand for either one of the standing blood pressure measurements due to dizziness or lightheadedness

Confirmed orthostatic hypotension is defined as initial assessment meeting the above orthostatic hypotension criteria confirmed by subsequent repeated assessments per protocol or if initial assessment met the above orthostatic hypotension criteria yet repeated assessments were not performed.

4.5.8. 12-Lead Electrocardiography

A standard 12-lead ECG will be performed according to the Schedule of Events in [Appendix 11.1](#) with the patient in the supine position for approximately 5 minutes and prior to blood samples being drawn. Heart rate will be recorded from the ventricular rate and the PR, QRS, and QT, QTc intervals, and ECG status (normal, abnormal not clinically significant or abnormal clinically significant) will also be recorded.

QTcF and QTcB are defined as follows:

$$\text{QTcF (ms)} = \text{QT} / \text{RR}^{1/3} \text{ and } \text{QTcB (ms)} = \text{QT} / \text{RR}^{1/2},$$

where QT is the uncorrected QT interval measured in ms, and RR is 60/HR with HR being the heart rate in beats per minute.

Potentially clinically significant values (PCSV) ranges will be applied to the ECG parameter values as applicable (see [Appendix 11.2](#) for PCSV definitions).

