#### 6.3.4.6. Assessment of Orthostatic Hypotension and Heart Rate

A blood pressure for the assessment of orthostatic hypotension will be conducted at the time points indicated in Section 6.1. The assessments should be conducted as per the instructions in the study manual. A patient will be determined to have orthostatic hypotension if any of the following criteria are met:

- If the supine blood pressure is  $<160$  mmHg systolic, a decrease in either the 1 or 3 minute standing systolic blood pressure of  $\geq 20$  mmHg or a decrease in the standing diastolic blood pressure of  $\geq 10$  mmHg from the supine systolic or diastolic blood pressure

OR

- If the supine blood pressure is  $\geq 160$  mmHg systolic, a decrease in either the 1 or 3 minute standing systolic blood pressure of  $\geq 30$  mmHg or a decrease in the standing diastolic blood pressure of  $\geq 15$  mmHg from the supine systolic or diastolic blood pressure

OR

- An increase in either the 1 or 3 minute standing heart rate of  $\geq 30$  bpm from the supine heart rate

OR

- The patient is unable to stand for either one of the standing blood pressure measurements due to dizziness or lightheadedness

If the initial assessment for orthostatic hypotension is consistent with the above definition, the supine and standing blood pressures and/or pulse should be repeated as outlined above, up to 2 more times.

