5.1.8.4. Analysis of Vital Signs

Vital signs (temperature, pulse, blood pressure, orthostatic blood pressure/heart rate, and respiration rate) will be summarized by baseline and change from baseline to each scheduled assessment time with descriptive statistics by treatment group and combined fasinumab for the SAF-LTS.

PCSV summary including orthostatic hypotension will be constructed for on-treatment period, post-treatment period and overall during the LTS study.

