SBP	≤ 95 mmHg and decrease from baseline ≥ 20 mmHg ≥ 160 mmHg and increase from baseline ≥ 20 mmHg	To be applied for all positions (including missing) except STANDING.
DBP	≤ 45 mmHg and decrease from baseline ≥ 10 mmHg ≥ 110 mmHg and increase from baseline ≥ 10 mmHg	To be applied for all positions (including missing) except STANDING.
Orthostatic Hypotension	Su SBP < 160 mmHg - SBP St – Su $\leq - 20$ mmHg DBP St – Su $\leq - 10$ mmHg Su SBP ≥ 160 mmHg - SBP St – Su $\leq - 30$ mmHg DBP St – Su $\leq - 15$ mmHg	
Weight	$\geq 5\%$ increase from baseline $\geq 5\%$ decrease from baseline	FDA Feb 2007.

Parameter	Treatment Emergent PCSV	Comments
ECG		Ref.: CPMP 1997 guideline. ICH E14 2005
HR	≤ 50 bpm and decrease from baseline ≥ 20 bpm ≥ 120 bpm and increase from baseline ≥ 20 bpm	
PR	≥ 220 ms and increase from baseline ≥ 20 ms	
QRS	≥ 120 ms & < 120 ms at baseline	
QTc	Absolute values (ms) > 450 ms and baseline ≤ 450 ms > 480 ms and baseline ≤ 480 ms > 500 ms and ≤ 500 ms at baseline Increase from baseline Increase from baseline 30-60 ms Increase from baseline > 60 ms	To be applied to any kind of QT correction formula. $\Delta QTc > 60$ ms are the PCSA to be identified in individual subjects/patients listings.

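### The orthostatic hypotension row in SAP Appendix 11.2 covers pressure falls only, so the vital-signs summary may give different counts from the primary safety variable built on SAP 4.5.7

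*SAP*

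**What the plan says.** SAP 4.5.1 lists among the primary safety variables "Incidence of confirmed orthostatic hypotension from baseline". SAP 4.5.7 supplies the definition, with the same four alternatives as Protocol 6.3.4.6. Two are pressure falls (at least 20 systolic or 10 diastolic if supine systolic is below 160 mmHg; at least 30 or 15 otherwise). The third begins "An increase in either the 1 or 3-minute standing heart rate" and requires a rise of at least 30 bpm. The fourth is "The patient is unable to stand for either one of the standing blood pressure measurements due to dizziness or lightheadedness".

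Confirmation has two routes in SAP 4.5.7. The first is "initial assessment meeting the above orthostatic hypotension criteria confirmed by subsequent repeated assessments per protocol". The second lets a positive stand without any repeat: "or if initial assessment met the above orthostatic hypotension criteria yet repeated assessments were not performed". The protocol's instruction after an initial positive is that "the supine and standing blood pressures and/or pulse should be repeated as outlined above, up to 2 more times".

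For vital signs, SAP 5.1.8.4 says "PCSV summary including orthostatic hypotension will be constructed for on-treatment period, post-treatment period and overall during the LTS study". The rule for that table is the orthostatic row of Appendix 11.2, Table 2, which opens "Su SBP < 160 mmHg - SBP St – Su" (St standing, Su supine). It gives the same four pressure thresholds and nothing else. SAP 5.1.7 sends all post-baseline data in the interval, scheduled and unscheduled, into the PCSV analysis.

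**The concern.** One clinical term is scored by two rules, and the SAP does not say how they relate. A patient too dizzy to stand at either time point has no standing pressure, so the PCSV rule has nothing to subtract and the patient is scored as a non-event. A patient whose only finding is a heart rate rise is missed as well. Conversely, a fall that the protocol's repeats cleared still counts in the PCSV table, because no confirmation step applies there.

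No other PCSV row fills the gap: the heart rate, systolic and diastolic rows in Appendix 11.2 are for all positions other than standing.

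Orthostatic assessment is one of the protocol's named tools for monitoring sympathetic nervous system dysfunction, which is an adverse event of special interest. A reader who sets the vital-signs summary beside the primary variable would find counts that may not match, with no explanation. Separately, SAP 4.5.7 does not say how many repeats must be positive, so two programmers could derive different primary counts from the same data.

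**Working it through.** The documents state no rate or count for this point, so there is no figure to reproduce. The check applies both rules to made-up patients.

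**Rules**
- SAP 4.5.7: positive if any standing reading shows a qualifying pressure fall or a heart rate rise of at least 30 bpm, or if a standing reading is impossible.
- Confirmed: initial positive, and either no repeat done or repeats positive (read two ways: any repeat, or all repeats).
- PCSV: positive if any reading shows a qualifying pressure fall.

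**Assumed readings**
- Supine 130/80, heart rate 70, so the 20/10 thresholds apply.
- Pressure fall: standing 108/76, heart rate 80. Systolic 130 − 108 = 22, at least 20: positive.
- Heart rate only: standing 126/78, heart rate 102. Falls 4 and 2, rise 102 − 70 = 32: positive under 4.5.7 only.
- Normal: standing 128/79, heart rate 75. Falls 2 and 1, rise 5: negative.

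| Profile | Confirmed (4.5.7) | PCSV (11.2) |
|---|---|---|
| Cannot stand at 1 or 3 minutes, no repeat | yes | no |
| Heart rate rise only, no repeat | yes | no |
| Fall at 1 minute, then cannot stand, no repeat | yes | yes |
| Pressure fall, never repeated | yes | yes |
| Pressure fall, both repeats positive | yes | yes |
| Pressure fall, both repeats normal | no | yes |
| Pressure fall, 1 of 2 repeats positive | yes if any repeat suffices; no if all must be positive | yes |

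The first two rows are events that only the 4.5.7 rule finds; the sixth is an event that only the PCSV rule finds. The last row shows the open repeat rule. The fourth row shows that counting unrepeated positives does not by itself separate the two rules for pressure falls.

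**Illustration of dilution in the primary count (assumed inputs only)**

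The main schedule has 15 post-baseline clinic visits with an orthostatic assessment: 13 at weeks 4 to 52 every 4 weeks, plus weeks 60 and 72. With false initial positives at a share p of visits and a share q of those not repeated, the share of patients counted through the unrepeated route is 1 − (1 − pq)^15, if visits are independent.

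- p = 1%, q = 10%: 1 − 0.999^15 = 1.5%
- p = 1%, q = 20%: 1 − 0.998^15 = 3.0%
- p = 3%, q = 30%: 1 − 0.991^15 = 12.7%

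Add these to assumed true rates of 4% and 2% (ratio 2.0, difference 2 points), taking none of the added patients to be true cases already:

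- 5.5 / 3.5 = 1.6
- 7.0 / 5.0 = 1.4
- 16.7 / 14.7 = 1.1

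The difference stays at 2 points throughout.

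**The case against.** **A reader might infer that two tables of one primary safety variable contradict each other.** The documents do not support that. Only the confirmed form is primary (SAP 4.5.1), expressed as events per 100 patient-years. The PCSV output is a separate vital-signs summary by period, and a screen of raw values will normally differ from a confirmed endpoint. What stands is that the screen also omits two protocol criteria, which confirmation does not explain.

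**A reader might infer that the clause on missing repeats is an error, or that it causes the mismatch.** It is an explicit convention that leans toward counting events, which is defensible in a safety study; removing those patients would treat a skipped repeat as a negative. For pressure falls it causes no mismatch, as shown above.

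**A reader might infer that unrepeated positives mask a signal.** The illustrated shrinkage of the ratio rests wholly on assumed rates. SAP 5.1.7.1 also reports the rate difference, which equal dilution in all arms leaves unchanged.

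**The appendix calls itself a reference**, with actual criteria to be agreed before database lock. But SAP 4.5.6 and 5.1.7 point to Appendix 11.2 for the PCSV definitions, and the appendix wants its criteria settled as part of the SAP, in light of the potential effects of treatment. The wording explains how the row came to be generic; it does not resolve the difference.

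**Patients unable to stand are not lost to the study.** They count in the primary variable, and Protocol 7.6.1.2 requires orthostatic hypotension to be entered as an adverse event. One with a qualifying 1-minute fall who then cannot stand also meets the PCSV rule. This limits the consequence to one table, and it stands. The heart rate criterion is likewise no SAP fault: it is copied from the protocol.

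**Conclusion.** The point holds as a definition mismatch in a safety summary. Followed as written, the Appendix 11.2 row scores as non-events patients with no standing reading or only a heart rate rise, and it keeps falls that were cleared on repeat. Its counts may differ from the primary variable in either direction. This assumes that initial and repeat readings are both in the database, which the confirmed definition itself requires.

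A smaller second point also holds: the number of positive repeats needed for confirmation is unstated, and the label covers cases that were never repeated.

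The frequency of these cases cannot be derived from the documents. Any effect on the rate ratio depends on false-positive and non-repeat rates that they do not give. The primary definition is not shown to be wrong, and no sample size, power or type I error is affected. It should be corrected before database lock because the correction is simple and the table would otherwise omit protocol-defined events.

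**What to change.** 1. Replace the orthostatic row in Appendix 11.2 with the SAP 4.5.7 criteria, and show the components in the 5.1.8.4 summary: pressure fall, heart rate rise only, unable to stand.
2. Keep the current confirmed rule as the primary count, and state in SAP 4.5.7 how many repeats must be positive.
3. Under that count, report positive on repeat and initial positive not repeated as separate rows.
4. Add a sensitivity count that excludes unrepeated positives other than inability to stand.

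The cost is SAP wording and a little more programming on data that the schedule already collects. The sensitivity count will be lower where sites skipped repeats; showing it beside the primary count makes that visible without dropping any event from the primary analysis.
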